### 7.1.3. Analysis Sets

There will be three analysis sets used in this study:

#### **Analysis Set #1:**

All subjects who undergo Model 4798 lead implant attempt procedure.

#### **Analysis Set #2:**

All subjects who are successfully implanted with a Model 4798 lead and with valid pacing data collected at 6 months post implant follow-up visit.

#### **Analysis Set #3:**

All subjects who are successfully implanted with a Model 4798 lead and who completed the 6-month post implant follow-up visit or experienced lead failure prior to 6-months.

If a subject experienced multiple Model 4798 lead implant procedures (e.g. a second lead was implanted due to a system modification of the initialed implanted lead), only first experience will be included for the analysis. Multiple lead attempts during this same procedure will not be counted as multiple procedures.

### 7.1.4. Primary Endpoints

#### **Primary Safety Endpoint**

The study primary safety endpoint is Attain Stability Quad MRI SureScan LV Lead (Model 4798) related complications through 6 months post implant. All reported system and procedure-related adverse events will be reviewed by an event review committee for LV lead relatedness and severity.

#### **Primary Efficacy Endpoint #1**

The Model 4798 LV lead has sixteen (16) programmable pacing vectors. The endpoint for the primary efficacy objective is whether there is at least one Model 4798 LV lead pacing vector with pacing capture voltage thresholds less than or equal to 2.5V (with absence of PNS at 5.0 V). This endpoint will be measured at the 6-month post implant follow-up visit.

#### **Primary Efficacy Endpoint #2**

The co-primary efficacy endpoint is whether a second Model 4798 lead configuration has a pacing capture threshold less than or equal to 4V (with absence of PNS at 5.0 V), excluding the pacing vector that is already counted to the primary efficacy endpoint #1. This endpoint will be measured at 6-month post implant follow-up visit.

---

 PCT measured at pulse width  $\leq$  0.5 ms

### 7.1.5. Secondary Endpoints

#### **To summarize implant procedure related information**

Implant procedure related endpoints will include implant success rate and procedure durations.

#### **To estimate 6-month reliability**

The Model 4798 LV lead 6-month reliability endpoint is Model 4798 lead related complications.

#### **To estimate electrical measurement values (PCTs and Lead Impedance) at 6 months post-implant**

The electrical measurements endpoints are pacing capture thresholds and impedance values collected at each time point (i.e. Implant, 6 months, etc.).

## 7.2. Center Pooling

The Attain Stability™ Quad Clinical Study is expected to be conducted at up to 56 sites worldwide, with a total enrollment of 471 subjects across all study centers. Participating geographies are expected to include, but are not limited to: the United States (US), Canada, EMEA, Malaysia, and Hong Kong. Per the CIP, each center will enroll between 0 and 50 subjects.

The primary analysis for all study objectives will include valid data entries from all study sites. In addition, sensitivity analysis will be conducted to assess in characteristics of each region and/or study site impact the overall study results. Specifically, this analysis will investigate whether sites exhibit significant heterogeneity in event rates, and whether geography (a binary variable representing whether a site is located in the US or outside United States (OUS)) moderates any statistically significant heterogeneity that is observed. Models will be fit separately for each primary outcome; in the analysis of each, centers within the US having  $\leq 5$  subjects with complete data will be considered as coming from one center, here denoted as 'US small'. Similarly, 'OUS small' will be the collection of data from centers outside the US having  $\leq 5$  subjects with complete data. If a Cochran's Q-test for heterogeneity shows  $p < 0.05$ , it will be taken as evidence of significant heterogeneity between sites. Evidence of between-site heterogeneity will not necessarily preclude pooling data; rather, it will prompt further investigation into the sources of the apparent differences in event rates between sites. At a minimum, findings of analyses on heterogeneity between study sites and between all US and OUS sites will be shown in the final report in a table by endpoint.

In addition, summary statistics for baseline characteristics and primary endpoints by study center may be provided in clinical reports. See examples below (actual format may vary).

Table A: Baseline Characteristics by Center				
Site	Number of Subjects Underwent Model 4798 Implant Attempt	Mean LVEF (<math>\pm</math> SD)	Mean QRS (<math>\pm</math> SD)	% Subjects with NYHA Class III/IV
Medical Center X				
Medical Center Y				
Medical Center Z				

Primary Objective Results by Site					
Site	Number of Subjects Underwent Model 4798 Implant Attempt	Number of Subjects implanted successfully with Model 4798 Lead	Number of Subjects with Model 4798 Related Complications through 6-months post-implant	% of Subjects with at least 2 vectors with PCT ≤ 4.0V	% of Subjects with at least one vector with PCT ≤ 2.5V
Medical Center X					
Medical Center Y					
Medical Center Z					

### 7.3. Handling of Missing Data and Dropouts

Unless otherwise specified, if data is missing then there will be no imputation of the data. Instead, subjects with missing data will be excluded. Survival analyses will consider time to event censored at the last contact for lost to follow-up subjects.

### 7.4. Adjustments for Multiple Comparisons

No adjustments will be made for multiple comparisons.

### 7.5. Demographic and Other Baseline Characteristics

Several characteristics will be reported for each enrolled subject at time of enrollment. The variables collected will include, but not limited to, subject age, gender, body mass index (BMI), left ventricular ejection fraction (LVEF), intrinsic QRS duration, New York Heart Association (NYHA) class and medical history. Tables and descriptive statistics will be used to summarize subject data with respect to these variables. For quantitative variables, the mean, standard deviation, median, first and third quartiles, minimum and maximum will be presented. For qualitative variables, counts and percentages will be given.

Sensitivity analysis will also be carried out using a similar method as outlined in section 7.2 to assess in subject gender affects overall study outcome.

### 7.6. Treatment Characteristics

Statistical summaries for treatment characteristic variables (on the LV Lead Implant Procedure CRF) will be reported. Continuous variables will be reported as mean, standard deviation, median, minimum, maximum, and quartiles. Categorical variables will be reported as number and percentage of subjects. The procedure variables to be summarized will include, but not limited to, CRT implant timing, operative time, LV lead implant timing, number of LV lead implant attempts, reason for being unable to implant the LV lead, diameter of the cardiac vein at final LV lead tip position, final location of LV tip electrode, final location of helix, final vector programmed for LV pacing configuration, reason for choosing final programmed vector.

## 7.7. Interim Analyses

The study protocol specified one non-formal interim analysis for secondary objective #2 (6-month reliability). See Section 7.8.4 for details. No formal interim analysis is planned for study primary objectives; or other secondary objectives.

## 7.8. Evaluation of Objectives

### 7.8.1. Primary Safety Objective

The Attain Stability™ Quad MRI SureScan LV Lead (Model 4798) will be considered safe if the probability of subjects free of Model 4798 lead-related complications at 6 months post-implant is greater than 87% (i.e., the lower bound of a one-sided 97.5% confidence interval must be greater than 87%).

Hypothesis:

$H_0: S_{(6\text{-month})} \leq 87\%$

$H_1: S_{(6\text{-month})} > 87\%$

where  $S_{6\text{-month}}$  is the probability that a subject remains free from Model 4798 lead related complications through 6 months since implant.

#### Analysis Dataset:

Analysis set #1 per section 7.1.3.

#### Analysis Method:

A standard time to first event survival analysis type will be performed to investigate the hypothesis proposed in the primary safety objective. More specifically, the Kaplan-Meier method will be used to estimate the probability of a subject surviving from any Model 4798 lead-related complication as a function of time; the 1-sided 97.5% confidence limit lower bound for the survival probability at 6 months (183 days) will be calculated using the log-log survival function approach (Kalbfleisch and Prentice 2002). For the purposes of this analysis, time 0 is defined as the day a subject undergoes the implant procedure of the Attain Stability Quad MRI SureScan LV Lead (Model 4798), which is independent of success status of this implant procedure. For the survival analysis, an event is defined as an Attain Stability Quad MRI SureScan LV Lead (Model 4798) related complication according to Clinical Events Committee (CEC) adjudication. Event date is the onset date of a subject's first complication that is related to the Attain Stability Quad MRI SureScan LV Lead (Model 4798). The definition of "complication" and "LV lead related" can be found on the study CIP. Subjects who undergo an Attain Stability Quad MRI SureScan LV Lead (Model 4798) implant attempt and do not experience any LV lead related complications will have their time to event censored at their last known time to exposure to the initial Attain Stability Quad MRI SureScan LV Lead (Model 4798). For any lost to follow-up subject, the last contact date will be used as the censor date.

#### Additional Analysis:

Sensitivity analyses will be performed to assess the robustness of the results. In particular,

---

 Kalbfleisch, J.D. and Prentice, R.L. (2002). *The Statistical Analysis of Failure Time Data*. Second Edition. John Wiley & Sons, Inc. New York.

- In the event a site investigator disagrees with the CEC's classification of an event, site investigator's event classification will be disclosed, however only CEC final adjudication results will be used for the statistical analysis. In the event when CEC final adjudication of relatedness of an event is "unknown", the "worst-case" scenario analysis will be carried out where the event will be counted as a lead related event in addition to the primary analysis of this objective.
- A tipping point survival analysis will be performed. In particular, subjects having time to event censored before 6 months will be considered one-by-one (by implant date) as observed events. Therefore, the 6-month survival intervals will be calculated for all scenarios in which a censored subject becomes an event.
- A similar survival analysis will be performed, but considering the first 200 subjects who had at least an implant attempt of the Attain Stability Quad MRI SureScan LV Lead - Model 4798. The first 200 subjects will be selected based on the date of implant. In case of a tie (for the 200th position) among subjects who are implanted on the same day, the initial procedure time (converted to U.S. central time) will be used to select the first 200 subjects.

### 7.8.2. Primary Efficacy Objective

To demonstrate the effectiveness of the Attain Stability Quad MRI SureScan LV Lead (Model 4798), the study will evaluate the likelihood that there are at least two programmable vectors for each patient post implant. The effectiveness of this lead will be evaluated based on two primary efficacy objectives. Both primary efficacy objectives must be met simultaneously.

#### **Primary Efficacy Objective #1**

The Attain Stability Quad MRI SureScan LV Lead (Model 4798) will meet this objective if the proportion of subjects with at least one LV lead pacing vector having a pacing capture threshold less than or equal to 2.5 V at 0.5 ms pulse width (with absence of Phrenic Nerve Stimulation (PNS) at 5.0 V) at 6 months post-implant is greater than 80%.

#### Hypothesis

H0: P16-month ≤ 80%

HA: P16-month > 80%

where P16-month is the proportion of subjects with pacing voltage thresholds ≤ 2.5V at 0.5ms (with absence of PNS at 5.0 V) at 6 months follow-up visit post-implant for at least one LV lead pacing vector.

#### **Primary Efficacy Objective #2**

The Attain Stability Quad MRI SureScan LV Lead (Model 4798) will meet this objective if the proportion of subjects having the two following conditions satisfied at the 6-month follow-up visit is greater than 80%:

- At least two LV lead pacing vectors having PCT less than or equal to 4.0 V at 0.5 ms pulse width and absence of PNS at 5.0V
- At least one LV lead pacing vector having PCT less than or equal to 2.5 V at 0.5 ms pulse width and absence of PNS at 5.0V

#### Hypothesis

H0: P26-month ≤ 80%

HA: P26-month > 80%

where P26-month is the proportion of subjects meeting the two conditions above.

**Analysis Dataset:**

Analysis set #2 per section 7.1.3.

**Analysis Method:**

The lower bound of the 1-sided 97.5% Confidence Interval for P16-month and P26-month will be calculated using the Clopper-Pearson method. More specifically,

- For the primary efficacy objective #1, the number of successes observed is defined as the number of subjects who had at the 6-month follow-up visit at least one vector with pacing voltage thresholds  $\leq 2.5V$  at 0.5ms and absence of PNS at 5.0 V.
- For the primary efficacy objective #2, the number of successes observed is defined as the number of subjects who had a) at least two LV lead pacing vectors having PCT less than or equal to 4.0 V and absence of PNS at 5.0V b) At least one LV lead pacing vector having PCT less than or equal to 2.5 V at 0.5ms and absence of PNS at 5.0 V.

For both objectives, only Model 4798 lead successfully implanted subjects who had the 6-month follow-up and performed the PNS testing will be considered.

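### A Model 4798 lead removed or replaced before 6 months for loss of capture, high threshold, dislodgement or PNS is excluded from both co-primary efficacy analyses instead of counting as a non-success

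*SAP*

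**What the plan says.** Section 7.8.2 assigns both efficacy objectives to "Analysis set #2 per section 7.1.3". Section 7.1.3 defines that set as "All subjects who are successfully implanted with a Model 4798 lead and with valid" pacing data from the 6-month visit; a footnote explains validity by pulse width. The analysis method in 7.8.2 then narrows the denominator to "only Model 4798 lead successfully implanted subjects who had the 6-month follow-up" and in whom PNS was tested.

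Section 7.3 gives the general missing-data rule: no imputation, and "subjects with missing data will be excluded". Section 7.1.1 says the same and promises an additional sensitivity analysis on missing data, without describing it.

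Two other parts of 7.1.3 matter. Analysis Set #3, used for the reliability objective, takes implanted subjects who "completed the 6-month post implant follow-up visit or experienced lead failure prior to 6-months". For a subject with more than one Model 4798 implant procedure, "only first experience will be included for the analysis".

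Each efficacy objective passes if the one-sided 97.5% Clopper-Pearson lower bound exceeds 80%, and both must pass.

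**The concern.** Section 7.8.2 introduces the efficacy question as how likely it is that each patient has at least two programmable vectors after implant. A lead taken out or exchanged because it lost capture, had high thresholds, dislodged or stimulated the phrenic nerve is close to a clear negative answer. Under Set #2 such a subject gives no answer at all.

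Whether a subject is excluded then depends on the outcome being measured, and the effect runs one way, towards a higher success proportion. The study has one arm and a fixed goal, so no control group offsets the bias. At stake are the error rate of the co-primary tests near the goal and, at any distance from it, the success proportion that is reported.

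**Working it through.** **1. Where each subject goes.** These cases concern a lead that fails for capture, threshold, dislodgement or PNS reasons before 6 months.

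| What happens to the initial lead | 6-month data on that lead? | Place in Set #2 |
|---|---|---|
| Removed, or replaced by another model | No | Excluded |
| Replaced by a second Model 4798 | No | Excluded, by inference from the first-experience rule |
| Repositioned | Yes, if tested at the visit | Kept; success or failure on the values measured then |
| Left in place, poor vectors | Yes, if tested | Kept; failure |

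The first two rows are the defect. Set #3 has the clause "or experienced lead failure prior to 6-months", which would keep them; Set #2 has nothing equivalent.

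**2. The plan's own figures (section 6, Table 1).** Enrolment = number needed at 6 months / (1 − 0.15):
- Efficacy #1: 145/0.85 = 170.6, so 171
- Efficacy #2: 50/0.85 = 58.8, so 59
- Overall: 400/0.85 = 470.6, so 471

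All three agree with the table. The SAP gives neither the true efficacy rates behind 145 and 50 nor a rate of early removal or replacement. Below, the share q removed or replaced for the listed reasons is an assumption, and 400 implanted subjects is an illustration.

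**3. The pass mark.** The lower bound for x successes in n is the 2.5% quantile of Beta(x, n − x + 1). At n = 400 the smallest passing count is 336 (84.0%, lower bound 80.03%), which allows 64 failures. At a true 80%, P(Bin(400, 0.80) ≥ 336) = 2.4%.

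**4. Chance of passing when the true proportion, with these events counted as failures, is exactly 80%.** Excluding a share q leaves n = 400(1 − q) subjects with success probability 0.80/(1 − q). The pass mark is recalculated for each n.

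| q | n | Success probability among those kept | Chance of passing |
|---|---|---|---|
| 0 | 400 | 80.0% | 2.4% |
| 2% | 392 | 81.6% | 10.6% |
| 3% | 388 | 82.5% | 19.4% |
| 4% | 384 | 83.3% | 37.1% |

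**5. Effect on a given result.** Counting the excluded subjects as non-successes multiplies the measured proportion by (1 − q).

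| Measured success | q | Excluded (lower bound) | Counted as non-success (lower bound) |
|---|---|---|---|
| about 85% | 2% | 333/392 = 84.9% (81.0%, passes) | 333/400 = 83.3% (79.2%, fails) |
| about 90% | 2% | 353/392 = 90.1% (86.7%, passes) | 353/400 = 88.3% (84.7%, passes) |
| 90% | 5% | 342/380 = 90.0% (86.5%, passes) | 342/400 = 85.5% (81.7%, passes) |

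With 400 implanted and 90% measured success, about 28 such subjects (28/400 = 7%) are needed to reverse the decision. At 88%, about 19 (19/400 = 4.75%) are needed.

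**The case against.** The strongest reply is that early lead failure already counts against the device. Any such event adjudicated as a lead-related complication enters the primary safety analysis (section 7.8.1), with time zero at the implant procedure and its own 87% goal. Section 7.1.1 also promises a missing-data sensitivity analysis. The tipping-point count in 7.8.2 lets a reader compare the failures tolerated with the revisions reported. All of this is true and limits the harm. None of it puts known failures into the efficacy proportions, which are tested separately. The tipping point works with hypothetical failures, and the 7.1.1 analysis is undefined.

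A second reply is that the decision changes only near the goal. That stands: a 5% share at 90% measured success alters the estimate but not the outcome.

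A reader might go further and infer that no rescued lead can ever be an efficacy failure, including one that was repositioned. The SAP does not support this. A repositioned lead still in place is scored on its 6-month vectors and fails if they miss the criteria. Nor is a good value after repositioning wrongly scored: the endpoint is status at the 6-month visit (sections 7.1.4 and 7.8.2), so the stated hypothesis is met. Making repositioning a failure in the primary analysis would change the endpoint.

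The second-lead case is also less certain than the others. The first-experience rule is printed beneath Set #3, and the SAP does not say how such a subject is scored in Set #2. Exclusion is the natural reading, but still an inference.

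**Conclusion.** The point holds for initial leads removed or replaced before 6 months for loss of capture, high threshold, dislodgement or PNS. These subjects drop out of both co-primary analyses, and both success proportions are biased upward relative to an endpoint that treats such a lead as a non-success. It does not extend to removal for unrelated reasons: removal for infection, for example, says little about thresholds.

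The size is unknown because the SAP gives no rate. Under the assumptions of 400 implanted, a true proportion of exactly 80% and every such event a failure, the nominal 2.5% error becomes about 11%, 19% or 37% at shares of 2%, 3% or 4%. These are boundary figures. Well above the goal, the consequence is an overstated proportion: at 90% measured success, 4.5 percentage points for a 5% share (90.0% against 85.5%).

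**What to change.** - **Section 7.1.3, Analysis Set #2:** add subjects whose initial Model 4798 lead was removed or replaced before the 6-month visit for loss of capture, high threshold, dislodgement or PNS. State that this includes replacement by a second Model 4798, so that nothing rests on inference.
- **Section 7.8.2:** count these subjects as non-successes for Objectives #1 and #2, and amend the sentence limiting the denominator to match. Leave removals for unrelated reasons excluded. Show the present completers-only result as a sensitivity analysis.
- **Repositioned leads:** state that they keep their 6-month score in the primary analysis, and add a sensitivity analysis counting them as non-successes.

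The cost is a change to the analysis definitions and a slightly lower reported success proportion. The sponsor should confirm that the case report forms or the adjudication record the reason for each removal or replacement, since the SAP does not show this.

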**Additional Analysis:**

Sensitivity analyses will be performed to assess the robustness of the results. In particular,

- A tipping point analysis will be performed to find how many more failures are necessary to not meet the primary efficacy objectives.
- Repeat these analyses using the first 200 subjects who are successfully implanted with a Model 4798 lead and have valid pacing data collected at 6 months post implant follow-up visit. In case of a tie (for the 200th position) among subjects who are implanted on the same day, the initial procedure time (converted to U.S. central time) will be used to select the first 200 subjects.

**7.8.3. Secondary Objective #1**

The first secondary objective is to summarize implant procedure information.

**Analysis Dataset:**

Analysis set #1 per section 7.1.3.

**Analysis Method:**

Descriptive statistics will be computed. The Attain Stability Quad LV lead implant success rate will be estimated as the number of subjects with Attain Stability Quad MRI SureScan LV Lead (Model 4798) successfully implanted divided by the total number of subjects who undergoes an Attain Stability Quad MRI SureScan LV Lead (Model 4798) implant attempt. A 2-sided 95% Confidence Interval will be calculated using the Clopper-Pearson method.

Procedure times are collected via eCRF. Only subjects with the Attain Stability Quad MRI SureScan LV Lead (Model 4798) successfully implanted will be included in this calculation.

- The total implant procedure time is defined as time from initial incision to final skin closure.
- Fluoroscopy time is defined as the total time the fluoroscope is imaging.
- Cannulation time is defined as the time from insertion of the first CS cannulation catheter to the first successful CS cannulation.
- Successful lead placement time is defined as the time from lead insertion of the successfully placed lead to the time when the lead is placed in its first acceptable pacing location. If a subject

experienced multiple implant attempts during the same procedure, only the final successful attempt will be included in this analysis.

Statistical summaries (e.g. mean, standard deviation, min, max, median) will be compute for these procedure times.

